14 ASSESSMENT OF OBJECTIVES / CRITERIA FOR EVALUATION

14.1 Safety Assessments

14.1.1 Specification of Safety Parameters

Safety will be assessed by reported AEs, physical examinations and vital signs (pulse, blood pressure, and temperature), laboratory measurements (haematology including coagulation, clinical chemistry, urinalysis, and faecal occult blood test), 12-lead ECGs, anti-dsDNA and ANA, thyroid gland (TPO, TSHR), anti-islet cells, anti-CCP, and Coombs test, anti-drug antibodies against BT063, and immunological status of potential viral and bacterial infections (hepatitis B and C virus, HIV, tetanus, diphtheria, tuberculosis as well as EBV/CMV serology).

14.1.2 Methods for Assessing, Recording and Analysing Safety Parameter(s)

14.1.2.1 Adverse Events

Safety and tolerability will be addressed by occurrence, frequency, nature, and severity of AEs. Adverse event and SAE assessments will be made throughout the study and will be evaluated and recorded in the source documents and on the eCRF as specified in [Section 14.3.2](#).

The seriousness, severity, and causality of each AE or SAE will be evaluated by the investigator in accordance with the definitions in [Section 14.3.1](#).

Subjects will be asked about AEs that occurred during the IV infusion or since the last visit by the use of non-leading questions.

Adverse Events of Special Interest

Adverse Events of special interest (AESI; serious or nonserious) are events that are of scientific and medical concern specific to the Sponsor's product for which close monitoring and rapid communication by the investigator to the Sponsor is appropriate. For this study, the following AEs of special interest will be recorded:

- Aphthous mouth ulcers (new, recurrent or aggravation of pre-existing lesions)
- Any other GI ulcers or significant GI symptoms (e.g., pain, blood in stool, dyspepsia or similar)

14.1.2.2 Physical Examination and Vital Signs

The investigator or qualified designee will perform a complete physical examination (genitourinary examination not required) at screening and baseline and then targeted physical examinations at the time points designated on the Flowchart of the Study ([Section 3](#)). Pre-dose abnormal findings will be recorded on the medical history eCRF. Any adverse change from the baseline physical examination (day 0 examination) will be documented on the AE eCRF. Weight will be measured at screening and the End of Treatment Visit only and height at screening only.

A full physical examination will include inspection of general appearance, skin, neck (including thyroid), eyes, ears, nose, throat, heart, lungs, abdomen, lymph nodes, extremities, musculoskeletal system, and nervous system.

Vital signs will be measured and recorded at the time points designated on the Flowchart of the Study (Section 3). The following measurements must be performed: systolic/diastolic blood pressure, pulse, and body temperature. Vital signs will be measured after the subject has been in the supine position for at least 5 minutes. All measurements will be recorded on the vital signs eCRF. Tests with abnormal results may be repeated at the discretion of the investigator and must be reported on the corresponding eCRF. When vital signs, ECGs, and/or blood sample collection occur at the same time, vital signs should be performed before ECGs and/or blood sample collection.

14.1.2.3 Laboratory Parameters

The tests listed in Table 14.1 will be conducted on samples collected and analysed by standard laboratory procedures at the time points designated on the Flowchart of the Study (Section 3). Tests that are not done must be reported as such on the eCRFs. Subjects should not eat or drink anything except water for 12 hours before the fasting glucose and fasting lipid tests at Visits 1, 2, and 12.

Sample handling, shipment, and assessment methods are described in the laboratory manual.

Table 14.1: Clinical Laboratory Tests

Haematology		
Haematocrit	White blood cell count with differential (neutrophils, eosinophils, lymphocytes, basophils, monocytes)	Coagulation (fibrinogen, prothrombin time, partial thromboplastin time)
Clinical Chemistry		
Alanine aminotransferase	Lipase	Urea
Aspartate aminotransferase	Bilirubin	Sodium
Gamma glutamyl transferase	Total protein	Chloride
Alkaline phosphatase	Albumin	Potassium
Lactic dehydrogenase	Creatinine	Calcium
ESR	CRP	
Urinalysis		
pH	Glucose	Urobilinogen
Blood	Ketones	Nitrites
Leucocytes	Bilirubin	Specific gravity
Protein		Microscopy

Table 14.1: Clinical Laboratory Tests

Other tests		
Thyroid stimulating hormone	Hepatitis B virus (hepatitis B virus polymerase chain reaction, hepatitis B surface antigen, hepatitis B surface antibody, total hepatitis B core antibody)	Tetanus (tetanus IgG antibodies, QuantiFERON®-TB Gold in-tube assay)
Free triiodothyronine		Diphtheria (IgG)
Free thyroxine		Epstein-Barr virus
Fasting glucose		Cytomegalovirus
Fasting triglycerides		
Fasting total cholesterol		Faecal occult blood test
Fasting high-density lipoprotein	Hepatitis C (hepatitis C polymerase chain reaction, hepatitis C viral RNA)	Pregnancy test or FSH assessment (females only)
Fasting low-density lipoprotein	HIV (anti-HIV1, anti-HIV2)	

All laboratory results have to be evaluated and results reported on the eCRF according to the following pattern:

- Outside reference range but not clinically relevant (e.g., due to already known conditions, due to sampling conditions, only marginal deviation, due to underlying diseases in the study population)
- Outside reference range and clinically relevant.

Laboratory values which are outside the reference range and assessed as clinically relevant) must be documented as AEs if they occur for the first time after administration of IMP.

If abnormal laboratory values are signs of an AE (e.g., an infection) that has already been reported during the study, that AE and not the laboratory value is all that should be reported.

14.1.2.4 *Electrocardiograms*

During the study, 12-lead ECGs will be performed at the time points designated on the Flowchart of the Study ([Section 3](#)).

The subject must be in a supine position in a rested and calm state for at least 5 minutes before ECG assessment is conducted. If the subject is unable to be in the supine position, the subject should be in the most recumbent position possible. All ECGs should be performed in a standardized method, in triplicate, and approximately 30 seconds apart, prior to blood draws or other invasive procedures. Each ECG must include the following measurements: QRS, QT, corrected QT, RR, and PR intervals.

The Principal Investigator or designated site physician will review and sign all ECGs. Results must be summarized in writing and classified as normal; abnormal; abnormal, clinically relevant; or abnormal, not clinically relevant. Once signed, the original ECG tracing will be retained with the subject's source documents. At the request of the Sponsor, a copy of the original ECG will be made available.

14.1.2.5 Auto-antibodies

The following auto-antibody titres will be determined from samples collected at the time points specified in the Flowchart of the Study ([Section 3](#)).

- Anti-dsDNA
- ANA
- TPO, THSR
- Anti-islet cells
- Anti-CCP
- Coombs test

Sample handling, shipment, and assessment methods are described the laboratory manual.

14.1.2.6 Anti-drug Antibodies

Antibodies to BT063 will be assessed from samples collected at the time points specified in the Flowchart of the Study ([Section 3](#)).

14.1.2.7 Immunological Status

The status of the following infections will be assessed from samples collected at the time points specified in the Flowchart of the Study ([Section 3](#)).

- Hepatitis B and C virus
- HIV
- Tetanus
- Diphtheria
- Tuberculosis (QuantiFERON® TB gold test)
- EBV/CMV serology

Sample handling, shipment, and assessment methods are described the laboratory manual.

14.1.2.8 Retention samples

The blood samples for immunological status of HBV, HCV, HIV, tetanus, diphtheria, tuberculosis, as well as EBV and CMV serology will be taken at baseline (V2, W0) and for follow-up (V14, W28) and stored at -20 °C or below, preferably below -65 °C, for up to 12 months after the end of the study for possible future testing.

Sample handling, shipment, and assessment methods are described in the laboratory manual.

14.2 Efficacy, Pharmacodynamic, and Pharmacokinetic Assessments

14.2.1 Specification of Efficacy Parameter(s)

Efficacy will be assessed at the times designated on the Flowchart of the Study (Section 3) using the following assessments:

- SLEDAI-2K
- CLASI
- BILAG score
- Tender joint count and swollen joint count
- Physician's Assessment of Disease Activity
- Subject Reported Outcomes: FACIT-F and SF-36v2 PCS
- ECLAM

14.2.2 Methods for Assessing, Recording and Analysing Efficacy Parameter(s)

Disease activity assessments for a particular subject should be performed (if at all possible) by the same assessor throughout the study to minimize inter-observer variation.

14.2.2.1 *Systemic Lupus Erythematosus Disease Activity Index 2000*

The SLEDAI-2K is a global index that measures SLE disease activity. It includes 24 items for the 9 organs/systems. Scores range from 0 to 105; a score of 6 is considered clinically important. The index measures disease activity within the last 10 days. The following activity categories and outcomes have been defined based on SLEDAI-2K scores:

SLEDAI-2K Score	SLE Activity
0	No activity
1 to 5	Mild activity
6 to 10	Moderate activity
11 to 19	High activity
20	Very high activity
Outcomes	
Reduction > 3 points	Improvement in SLE
Change of 1 to 3 points	Persistently active disease
Score of 0	Remission
Flares	
Increase > 3 points	Mild to moderate flare

Increase > 12 points	Severe flare
----------------------	--------------

The SLEDAI-2K will be administered at the time points designated on the Flowchart of the Study ([Section 3](#)). A sample SLEDAI-2K data collection sheet is presented in [Appendix C](#).

14.2.2.2 *Cutaneous Lupus Erythematosus Disease Area and Sensitivity Index*

The CLASI is an assessment over 13 body regions (scalp, ears, nose – incl. malar area, rest of the face, V-area neck – frontal, post. neck & shoulders, chest, abdomen, back and buttocks, arms, hands, legs, feet) and consists of 2 scores: total activity score and total damage score. Only the activity score will be used in this study. The activity score assesses erythema, scale/hyperkeratosis, mucous membrane involvement, acute hair loss, and non-scarring alopecia for each of body regions and the damage score assesses dyspigmentation and scarring, including scarring alopecia for each of regions. Higher scores indicate more disease activity. The grades associated with the CLASI are as follows:

Assessment	Score	Activity
Erythema	0	Absent
	1	Pink, faint erythema
	2	Red
	3	Dark red; purple/violaceous/crusted; haemorrhagic
Scale/Hypertrophy	0	Absent
	1	Scale
	2	Verrucous/hypertrophic
Dyspigmentation	0	Absent
	1	Dyspigmentation
Scarring/Atrophy/ Panniculitis	0	Absent
	1	Scarring
	2	Severely atrophic scarring or panniculitis

The CLASI will be administered at the time points designated on the Flowchart of the Study ([Section 3](#)). A sample of the CLASI is presented in [Appendix D](#).

14.2.2.3 *British Isles Lupus Assessment Group Score*

The BILAG 2004 index assesses lupus activity based on the physician's intent to treat. The index assesses conditions in 9 systems: constitutional, mucocutaneous, neuropsychiatric, musculoskeletal, cardiorespiratory, gastrointestinal, ophthalmic, renal,

and haematological. The use of the BILAG 2004 helps assess whether or not disease activity has resolved in 1 or more systems and whether or not there is new activity on other systems.

The index consists of 97 items. Some are rated as follows: 1 (improving), 2 (same), 3 (worse), and 4 (new). Others are recorded as values (e.g., blood pressure) or as Yes/No (e.g., accelerated hypertension). A graded score combining severity and perceived seriousness of the manifestation can be calculated manually or by a computer program. Overall scores per system are calculated as follows (the weighted numerical scores also make it possible to calculate a global score covering all 9 systems):

Score	Weighted Numerical Score	Findings and Treatments
A	12	Very active disease; treatment would include immunosuppressive drugs and/or an increased dose of prednisone > 20 mg/day or equivalent (including IV pulse methylprednisolone > 500 mg) or systemic immunomodulators (including biologicals, immunoglobulins, and plasmapheresis)
B	8	Moderate disease activity; use of lower dose corticosteroids, topical steroids, topical immunosuppressive drugs, antimalarials, or non-steroidal anti-inflammatory drugs - including low doses prednisone, intramuscular or intra-articular methylprednisolone, topical glucocorticoids or immunomodulators, antimalarials, thalidomide, prasterone, or acitretin
C	1	Mild stable disease; requires symptomatic therapy like simple analgesics
D	0	No disease activity but the system had been affected previously
E	0	No current or previous disease activity

A severe flare is defined as an increase of a previous score to an "A" and a moderate flare is an increase to a "B" score from C, D or E in any organ system.

Response is defined as loss of "A" and "B" scores in all systems without the development of any new "A" or "B" scores. Partial response is defined as a loss of "A" scores but with "B" scores persisting or developing while in a treatment.

The BILAG 2004 will be administered at the time points designated on the Flowchart of the Study ([Section 3](#)). A sample of the BILAG 2004 index is presented in [Appendix E](#).

14.2.2.4 Tender/Swollen Joint Count

A total of 66/68 joints will be assessed for the tender/swollen joint count. A joint that is normal (no tenderness or swelling) will be graded as 0. A joint with tenderness or swelling will be graded as 1. Higher scores indicate more disease activity.

The tender/swollen joint count will be assessed at the time points designated on the Flowchart of the Study ([Section 3](#)). A graphical presentation of the joints to be assessed is provided in [Appendix F](#).

14.2.2.5 Physician's Global Assessment of Disease Activity

The Physician's Global Assessment of disease activity is based on a 100 mm visual analogue scale (VAS) with the following range and increments ([Appendix A](#)):

Score	Definition
0	No disease activity
1	Mild disease activity
2	Moderate disease activity
3	Severe disease activity

The 100-mm scale will be provided to investigators who will make a vertical mark on the VAS indicating their assessment of the subject's disease activity. The distance along the line from 0 (no disease activity) to the mark will be measured and the number in mm will be recorded in the eCRF. Higher scores indicate more disease activity. The Physician's Global Assessment will be done at the time points designated on the Flowchart of the Study ([Section 3](#)).

14.2.2.6 Subject Reported Outcomes

Questionnaires on subject reported outcomes must be completed by the subject before any investigations or discussions about their disease with the study personnel.

SF-36v2 Physical Component Score

The SF-36v2 assesses the function status and well-being of subjects. The composite index includes 8 subscales: physical functioning, physical role functioning, bodily pain, general health perceptions, vitality, emotional role functioning, social role functioning, and mental health. For this study, the summary measure of the physical components (physical functioning, physical role functioning, bodily pain, and general health perceptions) will be used. Scores for each concept and overall scores for the physical and mental components are calculated according to the SF-36v2 manual. Higher scores indicate better quality of life.

The SF-36v2 will be administered at the time points designated on the Flowchart of the Study ([Section 3](#)). A sample SF-36v2 health questionnaire is presented in [Appendix G](#).

Functional Assessment of Chronic Illness Therapy-Fatigue

The FACIT system is a collection of quality of life measurements targeted to assess chronic illness. The Functional Assessment of Chronic Illness Therapy-Fatigue (FACIT-F) will be used in this study.

The FACIT-F consists of 5 areas: physical well-being, social/family well-being, emotional well-being, functional well-being, and additional concerns (fatigue).

The FACIT-F will be administered at the time points designated on the Flowchart of the Study ([Section 3](#)). A sample of the FACIT-F is presented in [Appendix H](#).

14.2.2.7 European Consensus Lupus Activity Measurement

The purpose of the ECLAM is to assess SLE disease activity within the past month. The measurement consists of 12 categories: generalised manifestations, articular manifestations, mucocutaneous manifestations, myositis, pericarditis, intestinal manifestations, pulmonary manifestations, neuropsychiatric manifestations, renal manifestations, haematologic features, erythrocyte sedimentation rate, and hypocomplementaemia. Scores range from 0 to 10 (scores higher than 10 are rounded off to 10) with lower scores indicating less disease activity.

The ECLAM will be administered at the time points designated on the Flowchart of the Study ([Section 3](#)). A sample of the ECLAM is presented in [Appendix I](#).

14.2.3 Pharmacodynamic and Pharmacokinetic Assessments

The analyses for PK and PD markers will be performed by a central laboratory or by central specialised laboratories.

14.2.3.1 Pharmacodynamic Assessments

The PD measurements will be analysed by standard procedures at the central laboratory or by central specialized laboratories. All final laboratory results from the central laboratory will be delivered electronically to [REDACTED] and loaded into the clinical database.

- Complement activity: C3, C4, CH50
- ESR and CRP
- Immunoglobulins: IgG, IgM, IgA, IgE
- Cytokines: IL-1 β , IL-2, IL-4, IL-5, IL-6, IL-8, IL-10, TNF- α , IFN- γ
- T- and B-lymphocytes: CD3, CD4, CD8, CD19, CD20, CD27, CD38, CD69, CD62L, HLA DR, CD45RA
- Free IL-10

Biomarkers

In order to explore systemic and local biological effects of BT063, biomarkers related to IL-10 biology and expected safety, efficacy, and mechanism of action of BT063 will be explored.

A quantitative, multiplex immunoassay for measurement of cytokines, chemokines, metabolic markers, hormones, growth factors, tissue remodeling proteins, angiogenesis

markers, acute phase reactants, cancer markers, kidney damage markers, central nervous system biomarkers and other important circulating proteins will be used.

Immunological Parameters

The following analyses are planned:

- Analysis of spontaneous dendritic cell maturation
- Analysis of IL-10 production by regulatory T-cells
- IL-10R expression and frequency of Th17 cell subsets
- Analysis of T cell homeostasis
- Cytokine concentrations in serum

14.2.3.2 Pharmacokinetic Assessments

To assess the serum level of BT063 over the course of the study, blood will be drawn pre-infusion and within 5 to 30 minutes after the 2-hour infusion on the following days: Day 0, Day 7, Day 14, Day 28, Day 42, Day 56, Day 70, and Day 84. In addition, blood will be drawn for PK assessments on Days 4 or 5, 91 (at least 5 days after last dosing), 98, 140, and 196. The actual PK sampling times will be captured in the eCRF.

The following PK measurements will be determined:

- Maximum serum concentration (C_{max})
- Time to maximum serum concentration (t_{max})
- Area under the concentration-time curve from time 0 to the last observable concentration at time t (AUC_{0-t})
- Elimination half-life ($t_{1/2}$)
- Apparent terminal-phase disposition rate constant (λ_z)
- Total body clearance from serum (CL)
- Apparent volume of distribution during the terminal phase (V_z).

14.2.4 Anticipated Blood Volumes

All subjects will provide blood for eligibility confirmation, safety, PK testing, and biomarker development throughout the study. The total anticipated blood volume to be collected is approximately 555 mL for each subject.

14.3 Adverse Events

14.3.1 Definitions

Adverse Event (AE)

Per ICH, an AE is defined as any untoward medical occurrence in a patient or clinical investigation subject administered a pharmaceutical product and which does not

necessarily have a causal relationship with this treatment. An AE can therefore be any unfavourable or unintended sign (including an abnormal laboratory finding), symptom, or disease temporally associated with the use of a medicinal (investigational) product, whether or not related to the medicinal (investigational) product. The AE may be any of the following:

- A new illness
- An exacerbation of a sign or symptom or the underlying condition or of a concomitant illness under treatment
- Unrelated to participation in the clinical study or an effect of the study medication or comparator drug
- A combination of 1 or more of the above factors

No causal relationship with the study medication is implied by the use of the term "adverse event."

Planned or elective surgical or invasive procedures for pre-existing conditions that have not worsened are not AEs. However, any complication that occurs during a planned or elective surgery is an AE. Conditions leading to unplanned surgical procedures may be AEs.

When an AE occurs after written consent has been obtained but before the first dose of study drug, the AE will be considered a non-treatment emergent AE. An AE that occurs from the time the subject receives his/her first dose of study drug until his/her last study visit will be considered a treatment-emergent AE regardless of the assessed relationship to the administration of the IMP.

For the recording of pregnancy and relevant laboratory data see [Section 14.3.2](#).

Immediately Reportable Adverse Event

Immediately reportable AEs (IRAEs) are AEs that must be reported to the Sponsor within 24 hours of the study site being informed of the IRAE (reporting requirements are detailed in [Section 14.3.2.1](#)).

Immediately reportable AEs include:

- All SAEs
- Overdose
- Pregnancy
- AEs that result in a subject's withdrawal from the study
- All AESIs ([Section 14.1.2.1](#))

Serious adverse event (SAE)

An SAE is any untoward medical occurrence or effect that at any dose:

- Results in death

- *Death is an outcome of an AE and not an AE in itself. All deaths, regardless of cause or relationship must be reported for subjects on study.*
- Is life-threatening
 - *Life-threatening means that the subject was at immediate risk of death from the event as it occurred. This does not include an event that might have led to death if it were more severe.*
- Requires hospitalization or prolongation of existing hospitalization
 - *Complications that occur during hospitalizations are AEs. However, if a complication prolongs hospitalization or requires new hospitalization, it is an SAE. In-patient hospitalization means the subject has been formally admitted to a hospital for medical reasons, for any length of time, which may or may not be overnight. It does not include presentation and care within an emergency department. If a subject experiences an AE during dosing and remains in hospital until the AE resolves, this is not considered an SAE unless the investigator considers that the event would have required hospitalization.*
- Results in persistent or significant disability or incapacity
- Is a congenital anomaly or birth defect
- Is another medically important condition

An important medical event that is not immediately life threatening or will result in death or hospitalization, but which may jeopardize the subject or may require medical intervention to prevent one of the outcomes listed above, should be reported as "serious" as well.

Medical and scientific judgment should be exercised in deciding whether a case is serious.

"Occurring at any dose" does not imply that the subject is receiving study drug at the time of the event.

Severity of Adverse Event:

Refers to the extent to which an AE affects the subject's daily activities. Severity will be categorized according to the following criteria:

Mild:	The AE does not interfere with the subject's routine activities.
Moderate:	The AE interferes with the subject's daily routine, but usual routine activities can still be carried out.
Severe:	The AE results in the inability to perform routine activities.

The term "severity" is used to describe the intensity of an event. This is not the same as "serious". Seriousness, not severity, serves as the guide for defining regulatory reporting obligations. The highest severity grade attained should be reported, for AEs with divergent severities.

Causality of Adverse Event:

Refers to the relationship of the AE to the study drug. Causality will be categorized according to the following criteria:

Not related:	Adverse events for which a reasonable explanation for an alternative cause is considered plausible, e.g., no study drug taken, plausible clinical alternative like accidental injury, expected progression of underlying or concomitant disease, pharmacologically incompatible temporal relationship, or intercurrent illness.
Related:	Adverse events for which a reasonably possible clinical and/or pharmacological relationship to study drug cannot be excluded, e.g., lacking plausible alternatives.

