14.3.2 Recording Adverse Events

Period: Subject Enrolment to the First Administration of Study Drug: Non-treatment emergent AEs will be recorded from the time when the subject is enrolled into the study (date of signature of the informed consent) until first administration of study drug.

Period: First Administration of Study Drug to Subject's last study visit: Thereafter all AEs are treatment-emergent AEs (TEAEs, see Definitions, [Section 14.3.1](#)) and will be recorded until the final follow-up visit has been performed.

Period after last study visit: Any SAE occurring after the subject's last study visit but considered by the investigator to be related to the study drug will be recorded.

If an AE (serious or not) started during the study but did not end before the final follow-up visit, the investigator should make a reasonable effort to establish the outcome and the end date. If this is not possible, the outcome recorded at the final follow-up visit will be assumed to be the final outcome.

If an event stops and later restarts, all the occurrences must be reported. Adverse events assessed as related to study medication by the investigator and all SAEs must be followed up until resolution.

Signs/symptoms should be documented if a definite diagnosis cannot be established. The investigator should attempt to establish a diagnosis of the event based on signs, symptoms and/or other clinical information. In such cases, the diagnosis should be documented as the AE and/or SAE and not the individual signs/symptoms. If a diagnosis is accompanied by unusual symptoms, the diagnosis itself and the symptoms have to be reported separately.

In addition to the definition as given, the following special types of events should be recorded:

- a) **Pregnancy** - Although not an AE per se, occurrence of pregnancy in a subject during a clinical study must be recorded.

b) **Laboratory values that are outside the normal range** and if, in the opinion of the investigator, these values represent a clinically relevant change versus pre-treatment values are also defined as AEs.

If abnormal laboratory values are signs of an AE (e.g., an infection) that has already been recorded, the respective abnormal laboratory value does not constitute a separate AE.

Wherever reasonable the reporting investigator will use the clinical term rather than the laboratory term (e.g., anaemia versus low haemoglobin value).

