15.2.4 Safety Analysis

The safety assessments for this study are the following:

- Adverse events (Including SAEs and AEs leading to discontinuation due to AEs)
- Physical examinations
- Vital signs
- ECGs
- Safety laboratory parameters (full blood count including white differential count, clinical chemistry, thyroid hormones, urinalysis, and faecal occult blood test)
- Development of anti-drug antibodies against BT063 (anti-BT063)
- Immunological status of potential viral and bacterial infections (HBV, HCV, HIV, tetanus, diphtheria tuberculosis)
- EBV / CMV Serology
- Premature withdrawals

Adverse events will be coded using the latest available version of the Medical Dictionary for Regulatory Activities (MedDRA®). Incidence rates (i.e., number and percentage of affected subjects) will be calculated for the coding levels system organ class and preferred term. Further analyses of AEs will focus on seriousness, intensity, causal relationship to study medication, and outcome. Serious adverse events will be displayed in detail.

Safety laboratory assessments will be categorized with respect to the laboratory specific reference ranges as normal/abnormal. Abnormal values will be further classified with respect to clinical relevance. Changes over time will be described by means of "shift-tables".

Observed values and change from baseline in 12-lead ECG parameters will be presented by treatment group. The number and percentage of subjects who had an overall impression status in category of normal, abnormal not significant, or abnormal significant will be summarized by treatment group.

Vitals signs parameters (systolic blood pressure, diastolic pressure, heart rate, and temperature) will be presented as a summary of observed and change from baseline values. Summaries for vital signs will be presented by visit and treatment group.

Safety analysis will be based on the safety population.

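### Adverse event severity is defined only by interference with daily activities, so a clinically relevant laboratory event without symptoms is always Mild and the intensity analysis cannot show how large it was

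*Protocol*

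**What the plan says.** Section 14.3.1 of the protocol defines the severity of an adverse event by a single criterion: it "Refers to the extent to which an AE affects the" everyday functioning of the subject. The three grades follow from it:

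- Mild is the absence of any such effect: "The AE does not interfere with the subject's routine activities"
- Moderate requires a disturbed routine that the subject can nevertheless keep up.
- Severe is the loss of that ability: "The AE results in the inability to perform routine activities"

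The same section treats severity and intensity as one thing and keeps both apart from seriousness. Sections 14.1.2.1 and 14.3.3.1 tell the investigator to use these definitions for every adverse event.

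Two passages make laboratory findings adverse events. Under section 14.1.2.3, out-of-range values judged clinically relevant "must be documented as AEs if they occur for the first time after administration of IMP". Under section 14.3.2, values outside the normal range count if, in the investigator's opinion, "these values represent a clinically relevant change versus pre-treatment values are also defined as AEs". Neither asks for a symptom.

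For the analysis, section 15.2.4 states: "Further analyses of AEs will focus on seriousness, intensity, causal relationship to study medication, and outcome".

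**The concern.** A functional scale works for events that the patient feels. Many laboratory events are not felt, at least at first. If the only question is whether daily life was disturbed, a modest and a profound asymptomatic fall in a blood count get the same answer and the same grade.

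At stake is one of the four named ways of looking at adverse events beyond their incidence. The trial plans no formal tests, so its safety conclusions rest on descriptive displays. Someone reading the intensity table would naturally take Mild to mean medically minor. For this class of event the table does not carry that meaning, and a difference between arms in the size of such events would not appear in it.

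**Working it through.** No arithmetic applies, because the point concerns a definition. The check is to follow one event through the rules and then see where its size could still be seen.

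**Which grade can it receive?**

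1. Take a hypothetical subject whose platelets fall from 120 to 20 x10^9/L without symptoms, a change the investigator judges clinically relevant. Platelets are in the scheduled safety laboratory panel (section 3, flowchart notes).
2. The fall is an adverse event under sections 14.1.2.3 and 14.3.2.
3. It must be graded by the section 14.3.1 definitions (sections 14.1.2.1 and 14.3.3.1). Laboratory events are not excepted.
4. Moderate needs interference with the daily routine, and Severe needs inability to carry out routine activities. Neither is present, so only Mild fits.
5. A much smaller fall, also judged clinically relevant and also without symptoms, gets the same grade by the same steps.
6. The intensity analysis in section 15.2.4 therefore shows both as Mild.

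**Does another rule rescue the grade?**

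- The instruction to report the highest severity attained does not help, because every grade attained is Mild.
- The clause allowing medical and scientific judgment concerns seriousness only.
- The protocol contains no toxicity scale and no laboratory thresholds for severity.
- If the abnormality does restrict activities, Moderate or Severe becomes available. The forced grade applies only where it does not.

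**Where can the size still be seen?**

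| Display | Shows the event? | Shows its size? |
|---|---|---|
| Incidence by system organ class and preferred term (15.2.4) | Yes | No |
| Intensity analysis (15.2.4) | Yes, as Mild | No |
| Detailed display of serious events (15.2.4) | If judged an important medical event | Case by case |
| Laboratory shift tables (15.2.4) | Yes | No; normal or abnormal, plus clinical relevance |
| Minimum and maximum values (15.2.2) | Yes | Extremes, by treatment group |
| Individual listings at the interim (15.2.8) | Yes | Yes |

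The shift tables are weakest when the baseline is already abnormal. The synopsis excludes platelets only below 50 x10^9/L, so a subject could enter at 60 and fall to 20. Assuming a lower reference limit above 60, that subject is abnormal before and after, and at most the relevance flag changes.

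**The case against.** The best case for the plan is that this is a deliberate choice. The protocol separates intensity from medical importance and makes seriousness the guide to regulatory reporting. An extreme laboratory value that endangers the subject should be reported as serious, and it would then be displayed in detail. Minimum and maximum values are summarised, and with 18 subjects in Part I the interim listings can be read line by line. Additional laboratory summaries could also be left to the analysis plan. The same scale applies in both blinded arms, so no bias in either direction is shown.

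Most of this stands, and it rules out several stronger readings:

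- A reader might infer that such an event is lost from the safety analysis. It is not: it is counted and can be found by the routes listed above.
- A reader might infer that the primary endpoint is compromised. That endpoint is incidence of adverse events, including serious ones and those leading to discontinuation; intensity is not part of it.
- A reader might infer that the Part II dose decision would be misled. Sections 8.1, 9 and 15.2.8 contain no decision rule that uses intensity grades, and the monitoring board receives unblinded data.
- A reader might infer from the high figure for haematological disease in section 6 that many such events will occur. That figure describes chronic anaemia, leukopenia and lymphopenia over the whole course of lupus. It is not a rate of new platelet falls over 28 weeks. Section 11.1.3 reports no BT063-related effect on lymphocyte values in the Phase I study and, in monkeys, minimal transient platelet rises rather than falls. The events of special interest are mouth ulcers and gastrointestinal events; for those that cause symptoms, a functional scale is workable.

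What does not stand is that these routes repair the intensity analysis. Seriousness depends on case-by-case judgment and leaves the grade unchanged. An analysis plan can add laboratory summaries, but it does not alter a grade the investigator has recorded under section 14.3.1. If investigators depart from the text and grade by judgment, the same value could be graded differently across the planned 12 to 15 sites.

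**Conclusion.** The point holds within narrow limits. Under the written definition, every clinically relevant laboratory event that leaves activities unaffected is Mild, so the intensity analysis carries no information about the magnitude of those events. That is a property of a rule this protocol fixes, not a detail awaiting the analysis plan.

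No numerical effect can be given, because the protocol does not state how many such events are expected. Adverse event incidence and expedited reporting are unaffected, and the size of individual abnormalities can be recovered from other displays. The conclusion assumes that investigators apply the definitions as written. It is a worthwhile correction to one safety table and does not threaten the trial's main safety result.

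**What to change.** In section 14.3.1, keep the functional scale for symptomatic events. Add that an adverse event consisting of a laboratory abnormality is graded by the size of the departure, using a pre-set published laboratory grading scale mapped to mild, moderate and severe. Three details should be settled with it:

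- How an abnormal baseline is handled, so that a subject who enters with a low count is not graded for the entry value alone.
- That the higher grade is reported where both the functional and the laboratory scale apply.
- That the rule also covers laboratory abnormalities recorded under a clinical term, since section 14.3.2 prefers anaemia, for example, to a low haemoglobin value.

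The cost is a short paragraph and a grading table in the protocol or laboratory manual; the laboratory values are already collected. The table must be agreed before unblinding. Because the monitoring board is due to see unblinded data once the third Part I subject reaches the End-of-Treatment visit, it is best fixed before then and used unchanged in both parts. The downside is that some events will move to a higher intensity class.
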